# **Health Education Model Led by Community Health Volunteers**

**NCT06312462**

**24-August-2025**

## **Study Protocol and Statistical Analysis Plan**

### **Study Design and Sampling**

A repeated cross-sectional design compared the impact of CHVs-led (CBPR-based) health education versus traditional health education on schistosomiasis-related KAP over 12 months (February 2024 - February 2025). The CBPR approach included: (1) Needs assessment using baseline surveys; (2) Co-design of interventions with community stakeholders; (3) Implementation led by trained CHVs; and (4) Mixed-methods evaluation combining infection rates and questionnaires(Figure 1). The process emphasized cultural adaptation, community ownership, and continued improvement to ensure sustainable interventions.

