### **Cluster Sampling Implementation**

A three-stage cluster sampling method was implemented:

1. School selection: Three public primary schools were randomly selected from distinct geographical regions of Pemba Island, matched for demographic characteristics (student population, gender ratio, and age distribution).
2. Cluster formation: Within each school, grades 4–6 (ages 8–16 years) were designated as natural clusters, reflecting the target population exposed to schistosomiasis transmission.
3. Participant inclusion: All students meeting eligibility criteria within selected grades were enrolled, minimizing selection bias through complete enumeration within clusters.

Intervention allocation:

- Intervention group: One school received CBPR-based education led by CHVs.

- Control group A and B: Two schools received standard health education from PHCs providers.

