## **Eligibility Criteria**

- Inclusion:
  - (1) Grades 4 – 6 students aged 8 – 16.
  - (2) Written parental/guardian consent and student assent.
  - (3) Permanent residency in the school's catchment area for  $\geq 2$  years.
- Exclusion:
  - (1) Severe cognitive or communication impairments affecting questionnaire completion.
  - (2) Temporary enrollment (e.g., visiting students).
  - (3) Missing consent documentation or incomplete questionnaires.

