## **Study design**

Baseline data were collected in February 2024, followed by a six-month intervention period. Post-intervention data were collected in August 2024, and a follow-up survey was conducted in February 2025 to assess the sustainability of the intervention effects. During the survey, face-to-face questionnaires were administered by CHVs to assess students' KAP related to schistosomiasis. Additionally, the research team distributed sterile wide-mouth plastic containers labeled with unique student identification numbers for morning urine sample collection. Each student provided approximately 30–50 mL of urine under teacher supervision to ensure proper collection procedures. The questionnaires, translated into Kiswahili, were pre-tested and validated. The questionnaire covered KAP of schistosomiasis transmission, exposure, and prevention. And include a survey on students' satisfaction with CHVs in the second questionnaire.

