## Statistical analysis

The data were double-entered into Microsoft Excel, systematically organized, coded, and verified for accuracy before being imported into IBM SPSS Statistics 26.0 for analysis. *S. haematobium* egg counts were stratified into light intensity (1–49 eggs/10 ml of urine) or heavy-intensity ( $\geq 50$  eggs/10 ml of urine) infection, based on WHO guidelines . For the KAP questionnaire: Knowledge scores were calculated based on correct responses (1 point per correct answer, maximum 10 points). Attitudes were evaluated using a 5-point Likert scale with a maximum score of 55 points. Behavioral patterns were scored according to frequency (1-3 points per item), totaling a maximum of 30 points. All scores were converted into percentage equivalents and categorized as "good" (80-100%), "moderate" (60-80%), or "poor" (<60%) . Satisfaction ratings were quantified with 1 point for "dissatisfied," 2 points for "neutral," and 3 points for "satisfied," yielding a maximum satisfaction score of 6 points.

Demographic and KAP data were analyzed descriptively: continuous variables were expressed as Mean  $\pm$  SD (normally distributed) or median [IQR] (non-normal). A two-way repeated-measures ANOVA with Bonferroni correction assessed temporal

effects (baseline/post-intervention/follow-up) and group differences. For ordinal data violating ANOVA assumptions (normality/homoscedasticity via Q-Q plots/Levene's test), the Kruskal-Wallis test was applied.

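### If pupils are linked across surveys, the three-wave repeated-measures ANOVA keeps only those seen every time, so the August 2024 contrast excludes pupils missing in February 2025

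*Combined protocol and SAP*

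**What the plan says.** The Statistical analysis section names one main inferential method for the scores: "A two-way repeated-measures ANOVA with Bonferroni correction assessed temporal" and then "effects (baseline/post-intervention/follow-up) and group differences". The data are "imported into IBM SPSS Statistics 26.0 for analysis", with no procedure named within that package.

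The Study design section dates the waves. "Baseline data were collected in February 2024", and "Post-intervention data were collected in August 2024, and a follow-up survey was conducted in February 2025". The last wave is there to show whether effects persist.

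Three other statements bear on who is in the model:

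- Study Design and Sampling opens with "A repeated cross-sectional design compared the impact of CHVs-led". That label does not by itself mean that the same pupils are measured each time.
- Eligibility Criteria lists as an exclusion "Missing consent documentation or incomplete questionnaires". It does not say whether a missed survey counts.
- Study design puts a pupil number on the urine containers. It does not say that questionnaires carry it or are matched across waves.

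The Kruskal-Wallis fallback is triggered by failed ANOVA assumptions, not by missing waves. The plan contains no mixed model, imputation, analysis population, expected absence rate or rule for a missed wave.

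**The concern.** A repeated-measures ANOVA with wave as a three-level within-pupil factor needs a value in every cell for every pupil, and the usual SPSS repeated-measures procedure removes incomplete cases listwise. Suppose a pupil took the whole course, completed both 2024 questionnaires, and then moved school or was absent on the February 2025 survey day. That pupil would leave the August comparison although both of the scores it needs are on file.

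Inclusion in the August contrast would then depend on something that happens six months after teaching ended. At the least this wastes data. If the pupils lost differ in score, and the loss differs between the one programme school and the two control schools, it also distorts the group contrast.

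The declared design adds a second problem. If the waves overlap only in part, the ANOVA discards every pupil outside the overlap. If they are not linked at all, it cannot be run.

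**Working it through.** The plan states no sample size, power, attrition or absence figure, so there is none to reproduce. The inputs from the plan are the model, the three waves and the allocation (one programme school, two control schools). Every rate below is an assumption.

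**1. Does the model need complete triples?** A repeated-measures ANOVA routine in another package (statsmodels) was given 20 simulated subjects at three waves with one value removed. It refused to fit, reporting unbalanced data. This is not SPSS, but it shows what the classical model requires.

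**2. Pupils kept.** Take pupils seen at baseline, with independent absence *a* at each of the two later waves. The ANOVA keeps (1−a)². The August contrast itself needs only baseline and August, so 1−a could be used.

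| a | Kept by ANOVA, (1−a)² | Usable for August, 1−a |
|---|---|---|
| 5% | 90.3% | 95% |
| 10% | 81.0% | 90% |
| 15% | 72.3% | 85% |
| 20% | 64.0% | 80% |

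**3. Questionnaires discarded.** Expected completed questionnaires per baseline pupil are 1 + 2(1−a), of which 3(1−a)² are used. The share discarded is 1 − 3(1−a)²/(1 + 2(1−a)). For a = 10% this is 1 − 2.43/2.80 = 13%; for 5% and 15% it is about 7% and 20%.

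**4. Power.** Assume 80% power at full numbers, two-sided 5%, ignoring school clustering. Power at retention r is Φ((1.960 + 0.842)√r − 1.960).

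- r = 0.90 gives 76%.
- r = 0.81 gives 71%.
- r = 0.64 gives 61%.

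At a = 10%, the avoidable loss for August is the step from 76% to 71%.

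**5. Bias, by hand.** Let a share p of August respondents be missing in February 2025, and let them have gained 0.5 SD less by August. The stayers' mean gain is then too high by 0.5p.

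- Programme school, p = 20%: 0.5 × 0.20 = 0.10 SD.
- Controls, p = 10%: 0.5 × 0.10 = 0.05 SD.
- Group contrast: 0.10 − 0.05 = 0.05 SD.

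Equal loss of the same kind in both groups gives zero.

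**6. Bias, by simulation.** 400,000 pupils per group, SD 1, within-pupil correlation 0.5, true August effect 0.50 SD. Where loss depends on the August score, low scorers are more likely to be lost.

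| Loss by February 2025 | Lost, programme v control | Effect, all pupils | Effect, stayers |
|---|---|---|---|
| Random | 20% v 20% | 0.502 | 0.502 |
| Score-related, same relation in both | 17% v 22% | 0.500 | 0.485 |
| Score-related in programme school only | 17% v 20% | 0.500 | 0.556 |
| Score-related in both, unequal rates | 25% v 12% | 0.503 | 0.545 |

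**7. Partial overlap.** Suppose the same grades 4–6 were surveyed again in February 2025, with equal grade sizes and one promotion in between. At most 2/3 = 67% of baseline pupils could have three waves, or 2/3 × 0.81 = 54% with 10% absence at each later wave. The plan does not say whether this happened.

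**The case against.** The strongest reply is that the plan declares repeated cross-sections and never says that questionnaires are linked, so a cohort with drop-out may not exist. This stands as a limit: the listwise argument is conditional on linkage. It does not rescue the plan, because the stated ANOVA presupposes linkage and fits neither alternative.

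A second reply is that listwise deletion is inferred. No SPSS procedure is named, and the package also has a mixed-model procedure that would keep these pupils. That is true, but the named method is repeated-measures ANOVA and nothing in the plan points to a mixed model.

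A reader might also infer more than the plan supports:

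- **That an absent pupil loses all data.** The loss is confined to the ANOVA. Descriptive summaries, egg-count classes and the Kruskal-Wallis fallback do not need three waves per pupil.
- **That the main result is damaged.** No section names a primary endpoint or time point. The comparison is framed over 12 months, and persistence to February 2025 is also an aim.
- **That the August effect is biased.** Random loss gives no bias, and score-related loss acting alike in both groups gives 0.485 against 0.50. The larger shifts need a difference between schools, of which the plan gives no evidence either way.
- **That the sampling claim is contradicted.** The phrase "minimizing selection bias through complete enumeration within clusters" concerns enrolment, not follow-up.

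The exclusion for incomplete questionnaires could be read as intending a complete-data population. If so, it confirms the restriction without justifying it for August.

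**Conclusion.** The point holds conditionally. If questionnaires are linked within pupil and the classical procedure is used, the August 2024 contrast rests on pupils also seen in February 2025, and nothing in the plan prevents this. The likely cost is precision: 90%, 81% or 72% of baseline pupils kept at 5%, 10% or 15% absence per later wave. Bias in the group contrast is a possibility rather than a finding. It is about 0.05 SD under the 20% v 10% illustration, and 0.045 to 0.056 SD in the two simulated cases where loss differed most by school. All these rates are assumed, so the true size cannot be computed from the plan. The conflict between the declared design and the model is in the text itself and needs resolving whatever the retention was.

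**What to change.** 1. Reconcile Study Design and Sampling with Statistical analysis by stating whether questionnaires are linked by pupil identifier, and whether the same pupils or the same grades were surveyed each time.
2. Where they are linked, replace the repeated-measures ANOVA with a linear mixed model (SPSS MIXED). Use group, wave and group-by-wave as fixed effects, with pupil as the repeated subject and an unstructured covariance over the three waves. Include every completed questionnaire from eligible pupils at each wave. For pupils who withdrew, use earlier data only as consent allows.
3. Report both the August 2024 and the February 2025 contrasts from this model, with three-wave complete cases as a sensitivity analysis.
4. Tabulate pupils seen at each wave by school, and compare the August scores of those seen and not seen in February 2025.
5. If the waves are unlinked, analyse them as independent samples with group-by-wave terms.
6. Say whether the exclusion for incomplete questionnaires applies to a single wave or to the pupil.

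The cost is revised wording and a different procedure on data already held, provided the identifiers exist. The document is dated after the last survey, so the change should be recorded as made after data collection. The mixed model assumes that missing waves are explained by the observed scores. It does not separate the programme from the single school that received it.

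### The February 2025 survey is meant to assess whether the effect is sustained, but the plan has only tests of difference and no estimate of how much of the August 2024 effect was kept

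*Combined protocol and SAP*

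**What the plan says.** The Study design section describes three waves: baseline in February 2024, a survey in August 2024 after six months of intervention, and a third wave, of which it says "a follow-up survey was conducted in February 2025 to assess the sustainability of the intervention effects". No other purpose is given for that wave.

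The Statistical analysis section plans descriptive summaries and one main inferential method. It states "A two-way repeated-measures ANOVA with Bonferroni correction assessed temporal", continuing with "effects (baseline/post-intervention/follow-up) and group differences". For ordinal data that violate the ANOVA assumptions, "the Kruskal-Wallis test was applied"; no multiplicity correction is stated for that fallback.

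The comparison is between one CHV-led school and two control schools. The documents do not define what would count as sustained, name a contrast for it, set a margin or retained share, plan a confidence interval, or give a sample size, SD, significance level or number of comparisons covered by Bonferroni.

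**The concern.** A test of difference asks whether there is evidence of change. A sustainability question asks whether there is evidence that the change was small, or how much of the effect is left. The planned methods leave two routes to an answer, and neither is adequate.

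- **August 2024 against February 2025.** This comparison can favour sustainability only by failing to reach significance. A smaller or noisier survey then helps the favourable conclusion, and so does a stricter threshold. Bonferroni protects against false claims of change, so it works the wrong way when no change is the welcome result.
- **February 2025 against baseline, or against controls.** A significant result shows that some effect is present. It does not say whether most of the August effect was kept or most of it lost.

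At stake is one of the two questions that the wave schedule exists to answer. Without an estimate of the loss, a statement that the effect lasted would have no controlled error rate. The point concerns the direction of the test and would remain if all waves fell in the same season.

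**Working it through.** **No figure to reproduce.** The plan states no sample size, power or margin. What follows illustrates direction and possible size under assumed inputs.

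**From the documents.** Three waves; one CHV school and two control schools; KAP scores expressed as percentages. The design is called repeated cross-sectional but the ANOVA is repeated-measures, so pupils may or may not be linked across waves. Both cases are shown.

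**Assumed.** Score SD 20 percentage points; true August effect 15 points; n pupils per school per wave; the two control schools pooled; pupil-level error only, which is optimistic; two-sided alpha 0.05; correlation r = 0.5 if linked and 0 if unlinked; a Bonferroni family of 3 (time pairs) or 9 (3 time pairs × 3 schools), applied to the difference-in-change contrast. The plan names neither this contrast, nor the pooling, nor the family.

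**Contrast.** Let E6 be the CHV-minus-control difference in change from February 2024 to August 2024, and E12 the same to February 2025. The loss is L = E6 − E12. Baseline cancels, so L is the difference in change between August and February 2025, with

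SE(L) = SD × √(2(1 − r)) × √(1/n + 1/(2n)).

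- n = 100, linked: 20 × √1 × √0.015 = 2.45
- n = 100, unlinked: 20 × √2 × √0.015 = 3.46
- n = 200, linked: 20 × √1 × √0.0075 = 1.73

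**Chance that a real loss is non-significant.** P = Φ(c − L/SE) − Φ(−c − L/SE), with c = 1.960 (alpha 0.05), 2.394 (0.05/3) or 2.773 (0.05/9). Half the effect lost is L = 7.5; one third lost is L = 5. The second term is negligible here. For example, with n = 100, linked, half lost: 7.5/2.45 = 3.06; Φ(1.960 − 3.06) = 14%; Φ(2.394 − 3.06) = 25%.

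| Scenario | Uncorrected | Bonferroni, 3 | Bonferroni, 9 |
|---|---|---|---|
| n = 100, linked, half lost | 14% | 25% | 39% |
| n = 100, unlinked, half lost | 42% | 59% | 73% |
| n = 100, linked, one third lost | 47% | 64% | 77% |
| n = 100, unlinked, one third lost | 70% | 83% | 91% |
| n = 200, linked, one third lost | 18% | 31% | 45% |
| n = 200, linked, half lost | 1% | 3% | 6% |

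**Check on a different contrast.** For August against February 2025 within one school, SE = SD × √(2(1 − r)/n). With n = 100, independent samples and a true fade of 0.2 SD: 0.2/√(2/100) = 1.414, so the fade is missed with probability Φ(1.960 − 1.414) = 71% uncorrected, Φ(2.394 − 1.414) = 84% over 3 comparisons and Φ(2.773 − 1.414) = 91% over 9. The direction is the same.

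**The other route.** If sustainability is read from a significant February 2025 superiority over baseline or controls, and no effect remains, the false-positive chance in the favourable direction is 0.05/2 = 2.5% uncorrected and 0.05/3/2 = 0.83% over 3 comparisons. Here Bonferroni is conservative. But this result controls only the claim that something remains.

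**The case against.** The strongest reply is that the plan contains no rule by which non-significance means sustained. A reader might infer that it would be read that way, but the documents do not say so; they give no rule at all. That reply stands, and the error described is therefore conditional on the reading.

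A reader might also infer that Bonferroni always pushes towards a false claim of sustainability. It does not. It does so for August 2024 against February 2025, and does the opposite for February 2025 against baseline or controls. Nor are all the planned tests stated to be corrected, since Kruskal-Wallis carries no stated correction.

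The size is open to challenge too. Sample size, SD, effect, correlation, pooling and family size are all assumed, and the results run from 1% to 91%. They show direction and plausibility, not the risk in this trial. If the planned descriptive summaries are tabulated by wave, a large fall would also be visible whatever its p-value.

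None of this supplies what is missing. Descriptive means carry no interval for the loss, and no planned test measures how much of the August effect remained.

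**Conclusion.** The concern holds in a limited form. The third wave has a stated aim that the planned tests cannot meet: they detect difference, and no contrast or interval measures retention. If a non-significant August-to-February comparison is taken as support, real fading can pass as sustained, and Bonferroni raises that chance for this contrast only. At 100 pupils per school, under the assumptions above, a loss of half the effect is missed 14% of the time uncorrected and 25% with a family of 3 if pupils are linked, or 42% and 59% if unlinked. With 200 linked pupils per school the same loss is rarely missed (1% and 3%). The documents do not give the figures needed to say where this trial lies.

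They do not support the stronger conclusions that the plan commits itself to the wrong inference or that the correction is harmful in general. The matter affects one stated aim, not the whole trial, and should be corrected.

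**What to change.** In the Statistical analysis section, for each KAP score, report from the same model E6, E12 and the loss E6 − E12, each as a CHV-minus-control difference in change with an uncorrected 95% CI. Then add that:

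- the sustainability statement rests on these estimates, and is made only where E6 itself shows an effect;
- a non-significant post-intervention versus follow-up difference is not evidence of sustainability;
- pupil-level intervals omit school-level variation, because the intervention arm is a single school ("Intervention group: One school received CBPR-based education led by CHVs"), so they are too narrow as statements about the programme.

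A fixed retained share, such as requiring the 95% CI for E12 − 0.5 × E6 to lie above zero, is not recommended. The documents give no share, and the document is dated after the last wave, so a share set now might be chosen with the data in view. The rule can also be met with nothing to sustain: with E6 = 0 and E12 = 5, n = 100 and linked pupils, the SE is 20 × √0.75 × √0.015 = 2.12, and the rule is met with probability Φ(5/2.12 − 1.96), about 65%.

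The cost is a few lines of text and contrasts on data already collected. The downside is that sustained becomes somewhat harder to claim.

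### The ordinal fallback, a one-factor Kruskal-Wallis test, cannot carry the group-by-wave contrast; if it compares banded KAP between schools at a later wave, a stable baseline gap can mimic or hide a programme effect

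*Combined protocol and SAP*

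**What the plan says.** Study Design and Sampling sets the question: "A repeated cross-sectional design compared the impact of CHVs-led (CBPR-based) health education versus traditional health education on schistosomiasis-related KAP". Study design gives three waves: baseline in February 2024, post-intervention in August 2024 and follow-up in February 2025.

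Statistical analysis gives the main method: "A two-way repeated-measures ANOVA with Bonferroni correction assessed temporal", continuing "effects (baseline/post-intervention/follow-up) and group differences". The interaction of group and wave is not named. The fallback follows: "For ordinal data violating ANOVA assumptions", judged by Q-Q plots and Levene's test, "the Kruskal-Wallis test was applied". No outcome, wave, grouping factor or change score is attached to it.

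KAP can reach this route, because "All scores were converted into percentage equivalents and categorized as" good, moderate or poor, which is an ordered three-level outcome.

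On the schools, Cluster Sampling Implementation says "Three public primary schools were randomly selected from distinct geographical regions of Pemba Island". They were matched on student numbers, gender ratio and age distribution. KAP is not among the matching variables. One school received the programme and two served as controls.

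**The concern.** With a baseline and two later waves, the programme effect is a difference in change: later minus baseline in the CHV school, less the same difference in the controls. A one-factor test cannot estimate this. Used across schools at a later wave, it ignores the baseline survey and tests the sum of the starting gap and the programme effect.

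Demographic matching does not make three schools from different regions equal on KAP. If the CHV school already scored higher, the test can be significant with no effect. If it started lower, a real effect can be missed.

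On the ANOVA route the interaction is available, so the gap there is narrower: nothing says that the interaction decides. The group main effect would be the wrong number to read. With starting gap d and effect D at both later waves it averages d, d + D and d + D, which is d + 2D/3.

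**Working it through.** The documents give no sample size, SD, baseline KAP or significance level, so there is no stated figure to reproduce. Every input below is assumed.

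**Inputs.** n = 100 pupils per school per wave; different pupils at each wave, the natural reading of a repeated cross-sectional design; latent normal score with SD 1; two-sided alpha 0.05; fallback triggered. Bands cut the latent score so that controls are 50/30/20% or 70/20/10% poor/moderate/good. d is the stable gap (CHV school minus each control) and D the programme effect. Ranges for bands span the two splits.

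**1. No effect, stable gap (bands, simulated with 3,000 runs).** Three-school Kruskal-Wallis at the post wave, against the post-minus-baseline contrast from a cumulative-logit model with group by wave:

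| Gap d | Kruskal-Wallis | Group by wave |
|---|---|---|
| 0.1 SD | 8-9% | about 5% |
| 0.2 SD | 19-25% | about 5% |
| 0.3 SD | 41-48% | about 5% |

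A separate simulation with other cut points and an F test of school by wave on the category scores gave 22% and 47% at gaps of 0.2 and 0.3 SD, and 4.6-4.9% for the interaction.

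**2. True effect D = 0.3 SD, CHV school starts lower (bands, controls pooled).**

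| Gap d | Kruskal-Wallis | Group by wave |
|---|---|---|
| 0 | 51-56% | 29-33% |
| -0.1 SD | 26-31% | 27-33% |
| -0.2 SD | 11-12% | 26-33% |

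The methods are about equal at -0.1 SD, and masking is clear at -0.2 SD. With no gap, Kruskal-Wallis has more power.

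**3. Closed-form check of the pattern on uncut scores.** Pooled-control Kruskal-Wallis has mean z = (d + D) × sqrt(3/π) / sqrt(1.5/n). For d + D = 0.1 / 0.2 / 0.3 the rejection rate is 12.6% / 35.8% / 66.8%. The group-by-wave contrast has mean z = D / sqrt(2 × 1.5/n) = 0.3 / sqrt(0.03) = 1.73, or 41.0%, whatever d is.

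**4. Schools that also drift apart.** Give each school an independent shock at the later wave with SD τ = 0.2. The contrast gains variance 1.5τ² = 0.06. Uncut scores, no programme effect, controls pooled:

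- Group by wave: sampling variance 0.03, total 0.09. The z statistic has SD sqrt(0.09/0.03) = 1.73, so it rejects in about 26%.
- Kruskal-Wallis, d = 0.1: sampling variance 0.015 × π/3 = 0.0157, total 0.0757. The z statistic has mean 0.1/sqrt(0.0157) = 0.80 and SD sqrt(0.0757/0.0157) = 2.20, so it rejects in about 40%.

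Both are far above 5%. If pupils were linked with within-pupil correlation 0.5, the group-by-wave figure would be about 38%, close to the 40%.

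**5. Trigger.** On bands, Levene's test alone fails in about 5-7% of runs with the 50/30/20 split and in roughly 36-71% with 70/20/10. The Q-Q plot criterion is a judgement and was not quantified. No overall trigger rate can be given.

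**The case against.** The strongest objection is that the harm depends on a use the plan never states. Kruskal-Wallis could compare waves within a school, or schools at every wave including baseline, which would expose a starting gap. It could also apply only to satisfaction with CHVs, which is ordinal and asked only in the second questionnaire. This stands: bias is possible, not shown. A reader might infer that the KAP results were in fact obtained from a later-wave comparison of schools, and the documents do not support that. But none of these uses tests the programme on ordinal KAP: waves within a school do not compare programmes, and separate tests at each wave do not test the difference in change.

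A reader might also quote the larger figures for uncut scores (three-school test: 10% / 28% / 56% at gaps of 0.1 / 0.2 / 0.3 SD). They apply only if scores are classed as ordinal. The plan points scores to the ANOVA, so the band figures are the ones to use.

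Third, the ANOVA can contain the interaction. That is right in principle, but a repeated-measures ANOVA needs the same pupils linked across waves, whereas the design is called repeated cross-sectional. Student identification numbers are mentioned only for the urine containers. The ANOVA interaction is therefore not a safe remedy for scores unless linkage is confirmed.

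Finally, the group-by-wave contrast costs power when there is no gap, and it does not cure the single intervention school. Both are true. The first advantage is earned only by assuming equal baselines, which demographic matching does not establish. The second limits the benefit but does not justify leaving in a gap that baseline data can remove.

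**Conclusion.** The point holds in conditional form. The fallback cannot carry the contrast that answers the study question, and its scope is unstated. If it is used on banded KAP between schools at a later wave, a stable gap of 0.2 SD raises the false-positive rate from about 5% to about 19-25%, and a gap of -0.2 SD cuts power for a 0.3 SD effect to about 11-12%, against 26-33%. At a gap of -0.1 SD the two methods have about equal power. The direction follows from the structure of the test. The sizes rest on assumed numbers of pupils, gaps, band splits and unlinked pupils, and on the fallback being triggered.

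The 5% should not be read as a guarantee for the group-by-wave contrast. It holds for stable gaps only, and under drift both methods exceed it.

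This should be fixed, with medium confidence: the defect and remedy are clear, but how and how often the fallback was used is unknown.

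**What to change.** - Name the group-by-wave contrasts as the test of the programme: post minus baseline and follow-up minus baseline, CHV school minus controls.
- State which variables, waves and grouping the ordinal fallback covers.
- For ordinal KAP outcomes measured at all waves, replace Kruskal-Wallis with a cumulative-logit model or a GEE containing group, wave and their interaction, clustered on pupil if pupils are linked.
- For scores, report the interaction from the planned repeated-measures ANOVA only if pupils are linked across waves. Otherwise fit a linear model with group, wave and group by wave to unlinked pupils.
- Keep Kruskal-Wallis for satisfaction, which has no baseline.
- Label the reanalysis as specified after data collection, and state that with one intervention school it removes only stable gaps; school-specific change over time remains confounded with the programme.

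The cost is SAP wording and a reanalysis of data already collected, with no new data. The cumulative-logit model needs a proportional-odds check. Power is lower when there is no baseline gap: for bands, unlinked pupils and an effect of 0.3 SD, about 29-33% against 51-56%.
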